2.4 Circumstances under which participants might leave the trial

We have no reason to anticipate that participants would have any adverse reaction to the intervention, but our experience of running singing and COPD projects suggests that individuals may decide to leave the singing group for the following reasons:

- Health problems associated with COPD or other conditions
- Health problems of spouse or partner or other family members
- Changes to other commitments which means that the day/time of the group no longer convenient
- Finding that the singing group is not what they expected

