2.2 Participants

In this study, the participant population will come from the population of COPD patients supported by the Respiratory Service of Medway Community Healthcare. Participants will be recruited from patients who have received PR and those who are currently undergoing PR. The study will seek to achieve a final sample of 80 patients at the second follow-up – 40 in the intervention arm and 40 in the control arm. The intention is to recruit 100 patients who consent to allow for 20% attrition. It is expected that we will need to secure initial expressions of interest from at least 120 people to allow for drop out even prior to consenting.

The number of participants is based on the resources available to run the trial, and no formal power calculation has been used to determine the sample size to be recruited. There is an important ethical issue raised by running a trial that is potentially under-powered. As Freedman et al. (2001:401) put it:

Sample size and power must be addressed before the start of a randomised, controlled trial. It is necessary to know in advance the likelihood of finding valid conclusions from the population assessed. It may be acceptable to subject a patient to a chance of a less than ideal treatment, or to the psychological stress of being a 'subject', if there is a chance of a valid scientific outcome, but it is not ethical to conduct a study the design of which cannot make valid conclusions.

However, relevant considerations are:

- There is no reason to think that participation in the trial will pose any risks to the participants, nor subject them to 'less than ideal treatment' or undue psychological stress. All of our experience with running previous studies in East Kent and Lambeth and Southwark, and the feasibility study in Medway is that participants will find the singing intervention enjoyable and personally and socially beneficial.
-
- The Brompton trials (Lord, 2010, 2012), involved 28 and 24 participants respectively, and reported significant changes in the physical component of the SF-36. The proposed study will be three times larger.
-

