2.8 Data Analysis

The design of the trial is a 3 by 2 mixed anova design with time as the within subjects factor at 3 levels (baseline, end of intervention and follow-up) and Condition as the between subjects factor with 2 levels (singing vs. control). The primary outcome variable for the trial will be the COPD Assessment Test score. Additional secondary analyses will consider a range of additional health measures, together with spirometry, exercise and SLP parameters. We will also examine differences between the intervention and control groups on indicators of service use to determine potential cost-savings associated with reduced inhaler usage, consultations with health professionals and hospital admissions. Embedded within the trial will be a qualitative assessment of the participant experience and perceived benefits, together with an evaluation of the resources to support practice between singing sessions.

Quantitative data

Quantitative data will be analysed using IBM SPSS 24. Comparative analysis will take place to examine composition of the intervention and control groups at baseline to assess equivalence. Comparisons will be made between the intervention and control groups at two follow up points to

determine whether the intervention has resulted in significant change on the primary and secondary outcome measures, which allow for rejection of the null hypothesis that singing results in no change in functional status, health related quality of life, mental wellbeing and patterns of breathing. Appendix 7.11 provides a plan for the statistical analysis to be undertaken, and considerations of effect size and power, provided by the project statistical consultant [name].)

Qualitative data

For the qualitative data obtained from individual interviews, thematic analysis (Braun and Clarke, 2006) will be used to identify any consistent themes. The qualitative data will be analysed using QSR International's NVivo 11 software. Within NVivo, queries will be run to determine word frequencies within respondents' qualitative comments.

For the thematic analysis, this process has six phases:

- Familiarising yourself with your data: Transcribing data (if necessary), reading and re-reading the data, noting down initial ideas.
- Generating initial codes: Coding interesting features of the data in a systematic fashion across the entire data set, collating data relevant to each code.

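### Section 2.4 blurs stopping singing with leaving the trial, and the fixed 3 by 2 repeated-measures ANOVA in its standard form discards six-month CAT scores from anyone who missed the second assessment

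*Protocol*

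**What the plan says.** **Leaving.** The heading of section 2.4 is "Circumstances under which participants might leave the trial". The text beneath it says that "our experience of running singing and COPD projects suggests that individuals may decide to leave the singing group for the following reasons" and gives four: the participant's own health, the health of family members, "Changes to other commitments which means that the day/time of the group no longer convenient", and "Finding that the singing group is not what they expected". The section describes no other way out of the trial.

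**Follow-up.** The Lay Summary says that assessments before the programme, after it and three months later are for all participants. Section 2.6 invites participants to three assessments and sets no attendance condition. The budget in section 5 covers 100 participants with three assessments each.

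**Sample.** Section 2.2 plans 100 recruits with 20% attrition: "The study will seek to achieve a final sample of 80 patients at the second follow-up", 40 in each arm.

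**Analysis.** Section 2.8 states that "The design of the trial is a 3 by 2 mixed anova design with time as the within subjects factor at 3 levels" and condition as the between-subjects factor. Section 2.1 says the same, and Appendix 7.14, titled as the statistical analysis plan, repeats the design and lists its simple effects. On software, "Quantitative data will be analysed using IBM SPSS 24". No covariate and no other model is named. Section 1.6 puts the primary endpoint at six months, which is T3, and section 2.7 stratifies randomisation by sex and COPD severity.

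**The concern.** Two things meet here.

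First, stopping an intervention and withdrawing from assessment are different events. A randomised comparison needs those who stop the intervention to remain in follow-up. Section 2.4 puts one event under the heading of the other. Staff who read it literally could stop inviting people who no longer sing. A reason such as disappointment with the group has no counterpart among controls, so any resulting loss could differ by arm.

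Second, the classical mixed ANOVA on three time points needs a complete row for each person. Someone with baseline and T3 scores but no T2 score is removed, although T3 carries the primary result. If loss is related to outcome and differs by arm, those who remain are no longer comparable as randomised. The model also leaves out the factors used to stratify randomisation.

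**Working it through.** **1. The plan's own numbers.** 80 / (1 - 0.20) = 100, which reproduces the recruitment target. The 40 per group behind the minimum detectable d = .68 in Appendix 7.14 is therefore the number left after attrition. (A one-sided level of .05/3 with 40 per group gives d = .674, close to that figure; a two-sided .05 gives .634.) Powering on the number expected to remain is ordinary practice and does not define an analysis set. It does show that loss is applied equally, 10 of 50 in each arm, whereas section 2.4 describes loss only from singing.

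**2. Heading against content.** Of the four reasons, the two health reasons could affect either arm. Finding the group not as expected requires being in the group. The timetable reason is also worded around the group's day and time. So at least one, and on its wording two, belong to the singing arm.

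**3. Observed T3 data not used.** If 80 people have a T3 score and a share m of them independently missed T2, the standard ANOVA uses 80 x (1 - m). The documents give no m, so the values below are assumed.

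| m (assumed) | People used | T3 scores discarded |
|---|---|---|
| 5% | 80 x 0.95 = 76 | 4 |
| 10% | 80 x 0.90 = 72 | 8 |
| 20% | 80 x 0.80 = 64 | 16 |

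**4. Possible bias.** If a share q of the singing arm is lost, and the T3 CAT of those lost is on average g points worse than that of those who stay, the mean of the stayers differs from the full-arm mean by q x g. Assume that control losses are unrelated to outcome. The 20% is the plan's overall attrition; treating all of it as selective in the singing arm is an assumption, and so is g.

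- g = 2: 0.2 x 2 = 0.4 points, which is 0.4 / 2 = 20% of the 2-point important change in section 2.1.
- g = 6: 0.2 x 6 = 1.2 points, which is 1.2 / 2 = 60% of it.

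For scale, section 2.2 equates 5 points with an effect of 0.5, which implies an SD of 5 / 0.5 = 10. With 40 per arm the standard error is 10 x sqrt(2/40) = 2.24. A shift of 1 point would then raise a two-sided 5% error rate to about 7.3%.

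This formula is for the raw T3 difference. In the time-by-condition interaction, which works on change, any part of g already present at baseline cancels.

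**5. Power is not the main issue.** If all 20 losses fell in the singing arm (30 against 50), the detectable d at two-sided .05 and 80% power would be .66, against .63 for 40 and 40. Uneven loss matters for selection more than for precision.

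**The case against.** A reader might infer that people who stop singing are counted as lost and that nothing keeps them in follow-up. The documents do not support that. Section 2.4 is a descriptive list with a mismatched heading. It sets no withdrawal rule and removes nobody. The Lay Summary, section 2.6 and the budget plan three assessments for everyone. Section 2.5 expects most people to attend at least 5 of the 10 sessions and does not exclude those who attend fewer. This objection stands, and it limits the first half of the point to unclear wording.

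A reader might also infer that the trial result will compare completers only. No sentence mentions complete cases. Section 2.8 plans comparisons at both follow-up points and Appendix 7.14 lists a condition effect within T3, which could be computed on everyone with a T3 score. Missing-data handling may also sit in a separate statistical analysis plan. That is fair, and silence on missing data is not the complaint. What remains is that the named model, in its standard form, needs all three scores, and that the protocol fixes it in three places with no alternative.

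The direction of bias is uncertain too. Section 3.5 foresees disappointed controls, who may also leave, and a relative's illness or a timetable clash need not track a participant's own CAT.

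**Conclusion.** The point holds in limited form and should be fixed. Section 2.4 blurs two events that the rest of the protocol appears to keep apart. The fixed ANOVA, run in its standard way, discards observed six-month CAT scores from anyone who missed T2, and it is open to bias if loss differs by arm.

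Neither the size nor the direction of the bias can be derived from the documents. The 0.4 to 1.2 points rest on three assumptions: 20% selective loss in the singing arm, a gap of 2 to 6 points, and outcome-unrelated loss among controls. The count of discarded scores rests on an assumed rate of missed T2 visits. Calling the defect fatal to the randomised comparison would go too far: assessment of everyone is already planned and funded, and the trial describes itself as a pilot.

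**What to change.** 1. In section 2.4, define two separate events: stopping attendance at singing, and withdrawing from the trial. State that people who stop singing are still invited to T2 and T3 and are analysed in the arm to which they were allocated.
2. In sections 2.1 and 2.8 and Appendix 7.14, replace the repeated-measures ANOVA with a linear mixed model (the MIXED procedure in SPSS). CAT at T2 and T3 are the outcomes; the terms are arm, visit and arm by visit, with baseline CAT, sex and COPD severity as covariates. Include everyone with at least one follow-up score, and take the T3 arm difference as the primary result.

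**Cost.** Wording changes, slightly more analysis work and some effort to invite non-attenders. The assessments are already budgeted: 100 x 3 x £50 = £15,000.

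**Limits.** The model assumes that data are missing at random given what it includes, and it recovers nothing for people with no follow-up. Continued follow-up of those who stop singing is therefore the main protection, and the model change comes second.

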2.5 Intervention and control

Following baseline assessments, participants will be randomly allocated to the control arm, which will be treatment as usual (TAU) following PR, or the intervention group, which will be TAU plus group singing.

There will be two intervention groups in the same community venue in the Medway district meeting on different days. Each group will consist initially of approximately 25 participants at the outset. The groups will be conducted by two experienced and skilled singing facilitators who are trained in facilitating breathing and singing techniques specifically for people with a respiratory disease. A total of 10 sessions will occur over the period of the study, with the expectation that most participants will attend a minimum of 5 sessions. Each session will be run for 90 mins with breathing exercises and singing occurring for one hour. The additional time will allow for the groups to socialise. Details of the programme are given in Appendix 7.12 together with a goals framework with details the links between activities and expected outcomes.

To complement the group singing, intervention participants will also be expected to practise the taught techniques away from the group. This home practice will be supported by a guide and video resources developed specifically for people with COPD. Choir facilitators will encourage use of the resources each week and ask participants to keep a diary of their use of the home programme.

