effect/analyses	expected difference	Notes	required N for minimum .80 power and alpha at .05 with moderate effect size d=.5		
anova - main effect of time	not relevant		34		
anova - main effect of condition	not relevant		86		
anova - interaction	significant		36		
anova - main effect of condition within T1	non significant		146	Bonferroni corrections included	sensitivity power analyses revealed that the minimum effect size detectable with power of .80 and sample size of 40 in each group is d=.68
anova- main effect of condition within T2	significant	the effect sizes of these two effects can be compared to test for prolonged effects of the intervention	146	Bonferroni corrections included	
anova - main effect of condition within T3	significant (but smaller than above)		146	Bonferroni corrections included	
anova - main effect of Time within Intervention Condition	significant		28		
anova - main effect of Time within TaU Condition	non significant		28		
anova - post hoc on main effect of Time within Intervantion Condition	significant between T1 and T2 but possibly disappearing between T2 and T3		39	Bonferroni corrections included	
anova - post hoc on main effect of Time within TaU Condition	not relevant		39	Bonferroni corrections included	

7.15 – Medway Singing and COPD Programme

The design of the singing programme is based on facilitator experience and participant feedback from singing for health projects conducted by the Sidney De Haan Research Centre over the past ten years. Each session will commence with physical and vocal warm-ups to prepare and protect the voice. These range in intensity and demand and are designed to provide a common focus, as well as encourage participants to learn to gain control of their breathing prior to singing.

Participants will be guided through a variety of songs, which gradually demand greater breath control and vocal production during the course of the singing sessions. Repertoire will include songs with short and long phrases, and a blended approach in each session will encourage confidence and breath-control. In addition, material will be utilised which encourages strong diction and vocal projection, both of which require consideration of breath control and management. Potential limitation in vocal range will be carefully addressed, with consideration given to the key and notation range in each song.

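### Singers are taught in two groups, but the tests and the detectable effect of d=.68 assume independent singers; any within-group correlation makes both too favourable

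*Protocol*

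**What the plan says.** Section 2.5 of the protocol sets up delivery in groups in one arm only. "There will be two intervention groups in the same community venue in the Medway district meeting on different days", and "Each group will consist initially of approximately 25 participants at the outset". On staffing it says "The groups will be conducted by two experienced and skilled singing facilitators", without saying whether the two lead jointly or take one group each. Sessions last 90 minutes, of which one hour is exercises and singing and the rest is social time. The other arm has no groups: "participants will be randomly allocated to the control arm, which will be treatment as usual (TAU) following PR".

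Section 2.2 aims for "40 in the intervention arm and 40 in the control arm" at the second follow-up. It also says "The intention is to recruit 100 patients who consent to allow for 20% attrition".

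Section 2.8 fixes the analysis: "The design of the trial is a 3 by 2 mixed anova design with time as the within subjects factor at 3 levels". Condition is the only other factor. Appendix 7.14, the statistical analysis plan, lists the tests and required sample sizes for that model. It marks the condition contrasts at T1, T2 and T3 as Bonferroni-corrected, gives N=146 for d=.5, and states that the "minimum effect size detectable with power of .80 and sample size of 40 in each group is d=.68". Singing group appears in no model term or power figure.

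**The concern.** The design is partially nested: singers belong to a group and controls do not. Singers in one group share a day, a session dynamic and social time. Appendix 7.15 counts bonding and security within the group among the ways the programme is meant to help with isolation and anxiety, so some similarity of outcome within a group is plausible. The mixed ANOVA handles the correlation of repeated measurements within a person. It does not handle correlation between people in the same group.

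If that correlation is positive, the mean of the singing arm is less precise than the analysis assumes. The tests exposed are those that compare the arms after randomisation or rely on variation among singers: the interaction, condition within T2 and within T3, and time within the intervention arm. Condition within T3 on CAT bears on the primary hypothesis in section 1.6, which is set at six months. Confidence intervals would be too narrow, and a result peculiar to one group could be read as an effect of singing.

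**Working it through.** **Inputs.** 40 analysed per arm and 20% attrition from 100 (2.2). Two singing groups (2.5), so m = 40/2 = 20 analysed per group. Power .80 and stated d=.68 (7.14). Assumed, because the protocol does not give them: ICC of .01, .02 and .05; clustering in the singing arm only; a Bonferroni family of three (T1, T2, T3).

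**Step 1: reproduce d=.68.** Independent-samples t-test (noncentral t), 40 per arm, power .80, no design effect:

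| Significance level | Detectable d | Total N for d=.5 |
|---|---|---|
| one-sided .05/3 cut to .016 | .678 | 146 |
| one-sided .05/3 | .674 | 144 |
| two-sided .05, uncorrected | .634 | 128 |
| two-sided .05/2 | .701 | 156 |
| two-sided .05/3 | .737 | 172 |

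Only the first row matches both stated figures (.68 and 146). Read as two-sided, the implied level would be about .031, which is .05 divided by 1.6 and so not a whole-number Bonferroni division. Either way the calculation assumes independent participants and contains no allowance for groups.

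**Step 2: variance with groups in one arm.** The variance of the singing-arm mean is multiplied by 1+(m−1)ICC and that of the control mean by 1. With equal arms, the variance of the difference is multiplied by

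[1+(m−1)ICC + 1]/2 = 1+(m−1)ICC/2 = 1+9.5×ICC.

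The standard error and the detectable d are multiplied by its square root.

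**Step 3: false-positive rate.** At two-sided .05/3 the critical value is z=2.394, so the true rate per contrast is 2[1−Φ(2.394/factor)].

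| ICC | Variance ratio | SE factor | False-positive rate (nominal .0167) | d from .68 | d from .737 |
|---|---|---|---|---|---|
| .01 | 1.095 | 1.046 | .022 | .71 | .77 |
| .02 | 1.190 | 1.091 | .028 | .74 | .80 |
| .05 | 1.475 | 1.214 | .049 | .83 | .90 |

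At ICC 0 every factor is 1 and nothing changes.

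**Step 4: power at d=.68.** By normal approximation with one-sided .05/3, power is .82 with no clustering, and .78, .745 and .65 at the three ICCs.

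**Step 5: why these are lower bounds.** Two groups leave one degree of freedom for between-group variance. With v1=(1+19×ICC)/40 on 1 df and v2=1/40 on 39 df, the Satterthwaite df are (v1+v2)²/(v1²/1+v2²/39) = 3.3, 2.9 and 2.3. The detectable effects above ignore this loss.

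The interaction and the time test within the singing arm are not quantified here. They depend on the ICC of change over time, which is a further unknown.

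**The case against.** **The size is assumed.** No ICC is given, and at ICC 0 the plan is correct. This stands: the direction holds for any positive ICC, but the amount is conditional. A reader might infer that the standard errors are shown to be too small; the protocol shows only that they would be if outcomes correlate within groups.

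**Not every test is touched.** A reader might infer that the whole table in 7.14 fails. It does not. T1 precedes randomisation and the forming of groups, and the time test within usual care and its post hoc comparisons involve no singers.

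**The contrasts are Bonferroni-corrected.** An uncorrected two-sided 5% test would have true rates of .061, .072 and .107, and a reader might take those as the error rates at T2 and T3. They belong to a test that 7.14 does not plan. At two-sided .05/3 each contrast stays below 5% over this ICC range. The inflation over .0167 remains.

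**The base figure is doubtful.** Scaling .68 to .71–.83 and stopping there would carry forward a figure that fits only a one-sided level. This stands, so both bases are shown.

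**Facilitators may not differ between groups.** Section 2.5 does not say who leads which group, and both groups use the same venue and programme. A facilitator effect cannot be assumed; the shared day and session remain.

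**It is a pilot, and d=.68 set nothing.** Section 2.2 bases the sample size on resources. This limits the consequence. But the plan tests hypotheses, and 2.2 foresees the results being taken into a larger trial.

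**A separate analysis plan could deal with it.** Appendix 7.14 is itself titled the statistical analysis plan, and it states the figure without an allowance.

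**Two groups are too few to model.** This is true, and it rules out a random group effect as a remedy. It does not make the unadjusted standard error right.

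**Conclusion.** The point holds in a limited form. The planned comparisons that involve singers after randomisation, and the stated d=.68, rest on independence among people taught together. Under ICCs of .01 to .05, with 20 analysed per group, 40 per arm and no clustering among controls, the between-arm standard error at T2 and T3 is understated by a factor of 1.05 to 1.21. If three two-sided tests share the 5%, the rate per contrast is .022 to .049 against .0167, so at the top of the range most of the Bonferroni protection is used up. The detectable effect is .71 to .83 from the plan's own base, or .77 to .90 from the two-sided base of .74, and these are lower bounds. The planned model need not be abandoned, but its precision should be reported with this limitation.

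**What to change.** Record each singer's group as a variable in the trial dataset; the data list in 2.6 and the home diary in 7.17 do not include it. Record also who led each group.

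Keep the planned model and add to Appendix 7.14:

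- For the CAT contrasts at T2 and T3, a pre-specified sensitivity analysis with the between-arm standard error multiplied by √(1+(m−1)ICC/2), m being the number analysed per singing group, for ICC .01, .02 and .05, at the plan's Bonferroni level. Report whether each conclusion survives.
- A descriptive table of CAT results by singing group.
- The sidedness and number of tests behind .68, and the detectable effect restated as a range over ICC: about .71 to .83 if the present one-sided base is intended, or about .77 to .90 if the tests are two-sided at .05/3.
- A note that two groups cannot estimate the ICC reliably and that the range is a lower bound.

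The cost is one variable, a few lines of text and a little more analysis. The stated detectable effect becomes less favourable. No more patients are needed.
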